5. ENDPOINTS

5.1 PRIMARY ENDPOINT

CTP: *Primary endpoint to assess safety and tolerability of BI 730357 is the number [N (%)] of subjects with adverse reactions.*

Please note that adverse reactions are defined and analysed as drug-related AEs.

5.2 SECONDARY ENDPOINTS

5.2.1 Key secondary endpoints

[figure not shown]
As no key secondary endpoints have been specified in the CTP, this section is not applicable.

[figure not shown]
5.2.2 Secondary endpoints

[figure not shown]
[figure not shown]
For the single rising dose (SRD) and the bioavailability (BA) part the secondary PK parameters are:

CTP:

- *AUC_{0-∞} (area under the concentration-time curve of the analyte in plasma over the time interval from 0 extrapolated to infinity)*
- *C_{max} (maximum measured concentration of the analyte in plasma)*

6. GENERAL ANALYSIS DEFINITIONS

6.1 TREATMENTS

SRD part:

In total, it was planned to include 72 healthy male volunteers in the SRD part of this trial. Each of the 10 sequential groups includes 8 subjects (6 active, 2 placebo) and is divided into two cohorts. The first cohort will be treated in a fixed sequence and the second cohort will be randomised.

In dose groups (DG) 1-7 and 10 each subject will receive one oral dose of BI 730357 or Placebo respectively at Visit 2, Day 1.

In DG 8 (400 mg/placebo with continental breakfast; Visit 2, Day 1) and DG 9 (400 mg/placebo with high-fat breakfast; Visit 3, Day 1) the same subjects will be included and treated with the same treatments (i.e. always with active or with placebo) for an intra-individual comparison of the two different diets (after washout period of at least 14 days).

BA part:

In total, it was planned to include 12 healthy male volunteers in the BA part of this trial. Each subject will receive BI 730357 as tablet (Tb) in a fasting state (reference treatment R), as oral solution (PfOS) in a fasting state (test treatment T1) and as tablet after a standardised high fat breakfast (test treatment T2) in an open label, randomised manner.

For details of dosage and formulation see [Table 6.1: 1](#) and [Table 6.1: 2](#) below.

Table 6.1: 1 Labels for treatments for use in the CTR (SRD Part)

Dose group	Treatment		Short label
1-10	M/N/U/V	Placebo solution / tablet, po, qd	Placebo total
1-7	M/N	Placebo solution / tablet, po, qd	Placebo fast
8	U	Placebo tablet, po, qd, fed continental	Placebo fed1
9-10	V	Placebo tablet, po, qd, fed high-fat	Placebo fed2
8-10	UV*	Placebo tablet, po, qd, fed continental/high-fat	Placebo fed
1	A	BI 730357, 1 mg/mL solution, 2 mg, po, qd	2mg PfOS fast
2	B	BI 730357, 1 mg/mL solution, 8 mg, po, qd	8mg PfOS fast
3	C	BI 730357, tablet, 25 mg, qd	25mg Tb fast
4	D	BI 730357, tablet, 50 mg, qd	50mg Tb fast
5	E	BI 730357, tablet, 2*50 mg, qd	100mg Tb fast
6	F	BI 730357, tablet, 4*50 mg, qd	200mg Tb fast
7	G	BI 730357, tablet, 8*50 mg, qd	400mg Tb fast
8	S	BI 730357, tablet, 8*50 mg, qd, fed continental	400mg Tb fed1
9	T	BI 730357, tablet, 8*50 mg, qd, fed high-fat	400mg Tb fed2
8-9	ST*	BI 730357, tablet, 8*50 mg, qd, fed continental/high-fat	400mg Tb fed
10	K	BI 730357, tablet, 16*50 mg, qd, fed high-fat	800mg Tb fed2

fed1 means intake of standard continental breakfast prior to drug administration

fed2 means intake of standard high-fat breakfast prior to drug administration

fed means intake of either standard continental or standard high-fat breakfast prior to drug administration

*: Placebo fed / 400mg Tb fed will be included in the same analyses in which within the BA part only the total group would be displayed, otherwise Placebo fed / 400mg Tb fed will be split into fed1 for subjects with continental breakfast and fed2 for subjects with high-fat breakfast

CTP: *The placebo control group in the safety evaluation will consist of all placebo treated subject, regardless of the dose group in which they were treated.*

This is applicable to the placebo control groups total, fast, fed1, fed2 and fed.

Table 6.1: 2 Labels for treatments for use in the CTR (BA Part)

Treatment		Short label
X (R)	BI 730357, tablet, 25 mg, fasted, qd	25mg Tb fast
Y (T2)	BI 730357, tablet, 25 mg, fed high-fat, qd	25mg Tb fed2
Z (T1)	BI 730357, 10 mg/mL solution, 25 mg, fasted, po, qd	25mg PfOS fast

Table 6.1: 3 Overview of treatments for intra-individual comparison

Study part	Test treatment (T)	Reference treatment (R)
SRD	400mg Tb fed2	400mg Tb fed1
BA	25mg PfOS fast (T1)	25mg Tb fast (R)
	25mg Tb fed2 (T2)	25mg Tb fast (R)

The following separate study phases will be defined for the analyses of AEs:

- **Screening** (ranging from 0:00 h on day of informed consent until administration time of study drug)
- **On-treatment**
SRD part:
DGs 1-7, 10: ranging from administration time of study drug until end of trial-termination date
DG 8 and 9: separately for each treatment, ranging from administration time of study drug until administration time of next study drug dose or end of trial-termination date
BA part:
separately for each treatment, ranging from administration time of study drug until administration time of next study drug dose or end of trial-termination date)

Please note that all AEs reported between start of trial drug administration and the last per-protocol contact will be considered on treatment (i.e. no follow-up period is considered in this trial).

Displays of AEs will be presented separately for the treatments described in [Table 6.1: 1](#) and [Table 6.1: 2](#). In the SRD part, the subjects in DG 8 and 9 will be handled separately, but counted only once in total.

Two types of AE displays will be provided in the report:

A) Section 15.3 (separate for SRD and BA part) and Appendix 16.1.9.2.8 (for ClinicalTrials.gov (separate for SRD and BA part) and EudraCT (SRD and BA part combined)) of the CTR displays:

In these displays, the on-treatment phase will be analysed (labelled with the name of the study treatment (short label)). Screening will not be included in this analysis.

The following totals will be provided in addition:

- a total over all BI-treated phases included in this analysis, DG A-G, S, T, ST and K ("Total BI")
- a total over all on-treatment phases included in this analysis ("Total on-treatment")
(Section 15.3 only)

B) Section 15.4 and Appendix 16.1.9.2.8 (except for ClinicalTrials.gov and EudraCT) of the CTR displays:

- Screening
- On-treatment (labelled with the name of the study treatment (short label))

In Section 16.1.9.2.8 AE tables (separate for SRD and BA part), the following totals will be provided in addition:

- a total over all study phases ("Total")

For detailed information on the handling of the treatments in the O*C views refer to Technical TSAP ADS (analysis data set) plan.

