Statistical methods: Descriptive statistics will be calculated for all endpoints. SRD part : Dose proportionality will be explored under fasted conditions using a regression model. A 95% confidence interval for the slope will be computed. BA part : Relative bioavailability will be estimated by the ratios of the geometric means (tablet / PfOS, tablet fed / tablet fasted) for the secondary endpoints. Additionally, their two-sided 90% confidence intervals (CIs) will be provided. Since the main focus is on estimation and not testing, an acceptance range was not specified. The statistical model will be an ANOVA on the logarithmic scale including effects for 'sequence', 'subjects nested within sequences', 'period' and 'treatment'. CIs will be calculated based on the residual error from ANOVA.				

FLOW CHART FOR THE SINGLE RISING DOSE PART

Visit	Day	Planned time (relative to drug administration [h:min])	Approximate clock time of actual day [h:min]	Event and comment	Safety laboratory	PK blood ^{10, 11}	PK urine ^{10, 12}	Blood sampling for biomarkers ^{10, 13}	12-lead ECG	Continuous ECG monitoring	Vital signs (BP, PR)	Questioning for AEs and concomitant therapy ⁶
1	-21 to -1			Screening (SCR) ¹	x				x ¹⁴		x	
2/3*	-3 to -1	-72:00 ⁷	08:00	Ambulatory visit	x							x
	1	-2:00	06:00	Admission to trial site in visits 2-3, allocation to treatment ² in visit 2 only	x ^{2,5}	x ²	x ²	x ²	x ^{2,9}	x ²	x ²	
		-0:30	07:30	Standard breakfast in dose groups 8-10 ¹⁶								
		0:00	08:00	Drug administration			▲			▲		
		0:30	08:30		x			x ⁹		x	x	
		1:00	09:00		x			x ⁹		x	x	
		1:30	09:30		x							
		2:00	10:00	240 mL fluid intake	x			x	x ⁹		x	x
		2:30	10:30		x							
		3:00	11:00		x			x ⁹		x	x	
		4:00	12:00	240 mL fluid intake, thereafter lunch ³	x ⁸	+	x	x ⁹		x	x	
		5:00	13:00		x			x ⁹		x	x	
		6:00	14:00		x	x		x	x ⁹	▼	x	x
		8:00	16:00	Snack (voluntary) ³	x	+		x ⁹		x	x	
		10:00	18:00	Dinner ³	x			x ⁹		x	x	
		12:00	20:00		x	+		x ⁹		x	x	
	2	24:00	08:00	Breakfast (voluntary) ³ , discharge from trial site	x	x	+	x	x ⁹		x	x
		34:00	18:00	Ambulatory visit	x			x ⁹		x	x	
	3	48:00	08:00	Ambulatory visit	x		▼	x	x ⁹		x	x
	4	72:00	08:00	Ambulatory visit	x	x					x	x
	5	96:00	08:00	Ambulatory visit	x			x			x	x
	8	168:00	08:00	Ambulatory visit	x ¹⁵	x		x				x
5	9 to 13			End of trial (EOT) examination ⁴	x				x ¹⁴		x	x

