* Only one treatment period (Visit 2) for dose groups 1-7 and 10. Two identical treatment periods separated by a wash-out phase of at least 14 days between drug administration for dose group (DG) 8 (Visit 2) and DG 9 (Visit 3). In DGs 8-9 the same subjects will be included.

1. Subject must be informed and written informed consent obtained prior to starting any screening procedures. Screening procedures include physical examination, check of vital signs, ECG (including rhythm strip of at least 15 minutes), safety laboratory (including drug screening), demographics (including determination of body height and weight, smoking status and alcohol history), relevant medical history, concomitant therapy and review of inclusion/exclusion criteria. Pharmacogenetic samples will be collected if needed.
2. The time is approximate; the respective procedure is to be performed and completed within 3 h prior to drug administration. Allocation to treatment may be performed at any time following enrolment but must be completed prior to (first) drug administration.
3. If several actions are indicated at the same time point, the intake of meals will be the last action.
4. End of trial examination includes physical examination, vital signs, ECG, safety laboratory, recording of AEs and concomitant therapies.
5. Only urine drug screening and alcohol breath test will be done at this time point.
6. AEs and concomitant therapies will be recorded throughout the trial, but will be specifically asked for at the time points indicated in the Flow Chart above.

Proprietary confidential information © 2017 Boehringer Ingelheim International GmbH or one or more of its affiliated companies

7. Safety laboratory to be taken and to be medically evaluated within 3 days prior to administration of study drug; this ambulatory visit including the safety laboratory can be omitted, if the screening examination is performed on Days -3, -2 or -1.
8. Two blood sample for stability testing will be taken at this time point (refer to Section [5.5.2.4](#))
9. The ECG recording has to be performed as triple at this time point
10. Sampling times and periods may be adapted based on information obtained during the trial (e.g. preliminary PK data) including addition of samples and visits as long as the total blood volume taken does not exceed 500 mL per subject
11. Including blood sample for metabolite identification (refer to Section [5.5.2.2](#))

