5.2.2.2 Adverse event collection and reporting

AEs collection

Upon enrolment into a trial, the subject's baseline condition is assessed (for instance, by documentation of medical history/concomitant diagnoses), and relevant changes from baseline are noted subsequently.

Subjects will be required to report spontaneously any AEs as well as the time of onset, end, and intensity of these events. In addition, each subject will be regularly assessed by the medical staff throughout the clinical trial and whenever the Investigator deems necessary. As a minimum, subjects will be questioned for AEs (and concomitant therapies) at the time points indicated in the [Flow Chart](#). Assessment will be made using non-specific questions such as 'How do you feel?'. Specific questions will be asked wherever necessary in order to more precisely describe an AE.

A careful written record of all AEs shall be kept by the Investigator in charge of the trial. Records of AEs shall include data on the time of onset, end time, and intensity of the event as well as any treatment or action required for the event and its outcome.

[figure not shown]
The following must be collected and documented on the appropriate CRF(s) by the Investigator:

- From signing the informed consent onwards through the residual effect period (REP), until an individual subject's end of trial:
 - All AEs (serious and non-serious) and all AESIs.
 - The only exception to this rule are AEs (serious and non-serious) and AESIs in Phase I trials in healthy volunteers, when subjects discontinue from the trial due to screening failures prior to administration of any trial medication. In

Proprietary confidential information © 2017 Boehringer Ingelheim International GmbH or one or more of its affiliated companies

these cases, the subjects' data must be collected at trial site but will not be entered in the CRF or trial database and will not be reported in the CTR.

- After the individual subject's end of trial:
 - The Investigator does not need to actively monitor the subject for AEs but should only report relevant SAEs and relevant AESIs of which [REDACTED] may become aware of.

The REP for BI 730357, when measurable drug levels or PD effects are still likely to be present after the last administration, is not known for this first-in-human trial. Therefore, all AEs reported until the end of trial examination (last per protocol contact) will be considered on treatment; please see Section [7.3.3](#).

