6.2.2 Treatment periods

Study participants will be admitted to trial site at least 1 hour prior to administration of the trial medication. They will be kept under close medical surveillance for at least 24 hours following drug administration. Thereafter the subjects will be allowed to leave the trial site after formal assessment and confirmation of their fitness. Afterwards the study will be performed in an ambulatory fashion until the end-of-study examination.

For DGs 1-7 and 10 of the SRD part, each subject will receive one dose of the respective trial medication (BI 730357 or placebo) at visit 2. In DGs 8 and 9 of the SRD part, the same subjects will be included and each subject will be treated with the same trial medication (either always active or always placebo), i.e. they will receive the respective trial medication at first in DG 8 (Visit 2) following a standard continental breakfast and in DG 9 (Visit 3) following a high-fat breakfast. The treatments of DG 8 and DG 9 are separated by a wash-out phase of at least 14 days between each drug administration.

The participants of the BA part will receive the respective trial medication (BI 730357) at visit 2, 3 and 4. Details on treatments and procedures of administration are described in Section [4.1.4](#).

For details on time points and procedures for collection of plasma and urine samples for PK analysis, refer to [Flow Chart](#) and Section [5.5.2](#).

The safety measurements performed during the treatment period are specified in Section [5.2](#) of this protocol and in the Flow Chart. For details on time points for all other trial procedures, refer to the Flow Chart. AEs and concomitant therapy will be assessed continuously from screening until the end of trial examination.

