7.3.3 Safety analyses

Safety analyses will be performed in accordance with BI standards.

All treated subjects (that is, all subjects who received at least one dose of study drug), will be included in the safety evaluation. Safety analyses will be descriptive in nature and will be based on BI standards.

Treatments will be compared in a descriptive way. The placebo control group in the safety evaluation will consist of all placebo treated subjects, regardless of the dose group in which they were treated. The active treatment groups will be compared to the placebo group in a descriptive way. Tabulations of frequencies/proportions will be used for the evaluation of categorical (qualitative) data, and tabulations of descriptive statistics will be used to analyse continuous (quantitative) data.

The analyses will be done by 'treatment at onset'.

Measurements (such as ECG, vital signs, or laboratory parameters) or AEs will be assigned to treatments (see Section [4.1](#)) based on the actual treatment at the planned time of the measurement or on the recorded time of AE onset (concept of treatment emergent AEs). Therefore, measurements planned or AEs recorded prior to first intake of trial medication will be assigned to 'screening', those between first trial medication intake until the end of trial visit will be assigned to the treatment period, and those after the end of trial examination will be assigned to 'post-study'. These assignments including the corresponding time intervals will be defined in detail in the TSAP.

Additionally, further treatment intervals (analysing treatments) may be defined in order to provide summary statistics for time intervals, such as combined treatments, on-treatment totals or periods without treatment effects (such as screening and post-study intervals).

Adverse events will be coded using the Medical Dictionary for Regulatory Activities (MedDRA). Frequency, severity and causal relationship of AEs will be tabulated by treatment, system organ class and preferred term. SAEs, AESIs (see Section [5.2.2.1](#)) and other significant AEs (according to ICH E3) will be listed separately.

Laboratory data will be compared to their reference ranges. Values outside the reference range as well as values defined as clinically relevant will be highlighted in the listings. Additionally, differences from baseline will be evaluated.

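### The SAP's on-treatment rule counts AEs for at least 14 days after the continental breakfast (DG 8) but only 8 to 12 days after the high-fat breakfast (DG 9): a minor, one-directional tilt in the descriptive AE tables

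*SAP*

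**What the plan says.** **Order and spacing.** Protocol 6.2.2 doses the DG 8/9 subjects "at first in DG 8 (Visit 2) following a standard continental breakfast and in DG 9 (Visit 3) following a high-fat breakfast". The order is not randomised. The footnote to the SRD Flow Chart specifies "Two identical treatment periods separated by a wash-out phase of at least 14 days between drug administration" and sets no upper limit. The same Flow Chart places the "End of trial (EOT) examination" on Day 9 to 13.

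**Counting rule.** SAP 6.1 sets the on-treatment phase for "DG 8 and 9: separately for each treatment, ranging from administration time of study drug until administration time of next study drug dose", or until the end-of-trial date. For DG 1-7 and DG 10 the phase runs from dosing to the end-of-trial date. No residual-effect cut-off applies. Protocol 5.2.2.2 explains that the residual effect period is unknown in this first-in-human trial, so "all AEs reported until the end of trial examination (last per protocol contact) will be considered on treatment". Protocol 7.3.3 leaves the detail to the SAP: "These assignments including the corresponding time intervals will be defined in detail in the TSAP".

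**What is counted and shown.** Protocol 6.2.2 states that "AEs and concomitant therapy will be assessed continuously from screening until the end of trial examination". The primary endpoint is the number of subjects with adverse reactions, and SAP 5.1 adds: "Please note that adverse reactions are defined and analysed as drug-related AEs". SAP 7.8.1 tabulates subjects with AEs and with drug-related AEs by treatment. SAP 6.1 and SAP 7 print DG 8 and DG 9 as separate columns. Neither document gives a common window or shows observation time per column.

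**The concern.** Diet is tied to visit, and visit decides how the AE phase ends. The continental phase is closed by the next dose and the high-fat phase by the end-of-trial examination. The first interval is longer in every subject who completes both visits, so the difference does not average out.

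If diet had no effect on AEs, the continental column would still be expected to show somewhat more subjects with AEs. A real increase after the high-fat breakfast would be somewhat understated. DG 8 is also out of line with the fasted 400 mg group (DG 7) and with DG 10, both of which close at the end-of-trial examination. The rationale for amendment 3 in Protocol Section 11 says that the fed groups were added to evaluate safety as well as PK, including the influence of food. A reader may therefore well compare these columns.

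**Working it through.** The plan states no figure on this point, so there is none to reproduce.

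**1. Window lengths.** The inputs are the SRD Flow Chart (dosing at about 08:00 on Day 1, end of trial on Day 9 to 13), the washout of at least 14 days, and the SAP 6.1 phase rule. On the Flow Chart's clock, Day d is d − 1 days after dosing (Day 8 is printed as 168 h). I take Day 9 to 13 as counted from the last dose.

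- DG 8: at least 14 days.
- DG 9: 9 − 1 = 8 days to 13 − 1 = 12 days. If the phase runs to midnight of Day 13, add 16 h: 12.67 days.
- Ratio: at least 14/8 = 1.75, 14/12 = 1.17 or 14/12.67 = 1.11.
- Unmatched days: at least 14 − 8 = 6 down to 14 − 12.67 = 1.33, or 43% to 10% of a 14-day window.
- Six active subjects: at least 6 × 14 = 84 subject-days versus 6 × 8 = 48 to 6 × 12.67 = 76.

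**2. Are the extra days observed?** Yes. AE assessment is continuous. The Flow Chart also schedules AE questioning and a safety laboratory within 3 days before the Visit 3 dose, which is 11 days or more after the DG 8 dose and so inside the continental phase.

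**3. Is the fixed order the cause?** The BA part uses the same phase rule but six randomised sequences. If its 12 subjects split evenly (2 per sequence), each treatment is last in 2 × 2 = 4 of 12 subjects, so window length is not tied to one treatment.

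**4. Which comparisons are matched?** Placebo fed1 consists of DG 8 placebo subjects only, so active versus placebo within DG 8 has equal windows. Placebo total mixes window lengths.

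**5. Illustrative size.** The documents give no AE rate. Assume a constant onset rate h per day, equal for both diets. Expected subjects with an AE out of 6 = 6 × (1 − exp(−hT)). The chance that at least one DG 8 subject is counted only because of the unmatched days is 1 − (1 − q)^6, with q = exp(−h·T9) − exp(−14h) and T9 the DG 9 window.

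| h per day (assumed) | DG 8, 14 d | DG 9, 8 to 12.67 d | Chance of an extra DG 8 subject |
|---|---|---|---|
| 0.25% | 0.21 | 0.12 to 0.19 | 8% to 2% |
| 1% | 0.78 | 0.46 to 0.71 | 28% to 7% |
| 2% | 1.47 | 0.89 to 1.34 | 46% to 12% |

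The lowest row is the more plausible one for drug-related AEs. The other two are closer to AEs of any cause.

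**6. If onset declines after dosing.** Suppose instead that the onset rate halves every 2 days. The share of a 14-day window's events that start between 8 and 14 days is (2^−4 − 2^−7)/(1 − 2^−7) = 5.5%. For 12 to 14 days it is (2^−6 − 2^−7)/(1 − 2^−7) = 0.8%. Under a constant rate the shares are 6/14 = 43% and 2/14 = 14%.

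**The case against.** The strongest case on the other side accepts the arithmetic and disputes the consequence. Most of it stands.

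- **Subjects are counted, not events** (SAP 7.8.1). A late AE changes a count only if that subject had no earlier qualifying AE. A reader might infer that every AE in the unmatched days adds to the DG 8 column. It does not.
- **Onset time feeds causality.** Protocol 5.2.2.1 lists a plausible time to onset as an argument for relatedness and its absence as an argument against. Late events after a single dose are therefore the least likely to enter the primary endpoint.
- **The stated safety comparison is active versus placebo, descriptively** (Protocol 7.1.1 and 7.3.3). The modelled comparison of the two diets concerns AUC and Cmax only (SAP 7.5.2).
- **The open window is deliberate.** With the residual effect period unknown, counting to the last contact is reasoned. A late AE before Visit 3 is also correctly attributed, because only the continental dose has been given.
- **Much can be traced.** Dosing times and individual data are listed, and each column has six active subjects. AE summarisation rules in the sponsor's guidelines are not available here.

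What remains is that the two diet columns are printed separately, with unequal windows that always differ in the same direction, and nothing in the tables tells the reader so.

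**Conclusion.** The asymmetry is real and follows directly from the documents: at least 14 days against 8 to 12 (at most 12.7) in every subject who completes both visits. If a subject leaves after Visit 2, the end-of-trial date closes the DG 8 phase instead. Reading DG 8 against DG 9, or against the other dose groups, is tilted towards more subjects with AEs in DG 8. This matters mainly for the all-AE tables and is probably small for the primary endpoint. Any size in subjects rests on an assumed rate: 0.21 versus 0.12-0.19 of 6 at a constant 0.25% per day, and less if onset declines after dosing.

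Stronger readings are tempting but not supported:

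- A reader might infer that the primary endpoint is materially biased, or that a true high-fat increase would appear as a decrease. That needs a constant all-cause rate of about 1% per day and the shortest DG 9 window. The documents give no such rate, and their causality criteria point the other way for late events.
- A reader might infer that dose escalation is affected. Protocol 3.1 bases those reviews on AEs up to at least 48 h after dosing as a minimum, so the table window does not drive them.
- A reader might extend the point to the PK ratio. That ratio shares the fixed order, but it does not depend on the AE phase rule.

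Severity: minor.

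**What to change.** In SAP 6.1 and 7.8.1:

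1. Keep the full-window AE tables as defined, and add the median and range of observation days per column.
2. Add one supplementary by-treatment table for the SRD part: subjects with any AE and with drug-related AEs, with onset from dosing to 168 h, in every dose group. At 168 h the Flow Chart schedules AE questioning before the earliest end-of-trial day, so the window is the same for all columns.
3. State that AEs starting after 168 h remain in the full-window tables, totals and listings.

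Dosing order, AE collection and the PK model stay as they are. The cost is one extra table and one row of observation days, from dosing and onset times already recorded. The downside is that AEs starting after 168 h, including some in days that both diets share, appear only in the full-window tables and listings. Six active subjects per column also remain few.
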